## 7. 6 STUDY INTERVENTION(S) OR EXPERIMENTAL MANIPULATION(S)

### 1. 6.1 STUDY INTERVENTION(S) OR EXPERIMENTAL MANIPULATION(S) ADMINISTRATION

#### 1. 6.1.1 STUDY INTERVENTION OR EXPERIMENTAL MANIPULATION DESCRIPTION

The BE WITH program is grounded in (1) the Befriending and Narrative Reminiscence literature which are best practices in working with older adults, and (2) the Interpersonal Psychological Theory of Suicide (ITPS). BE WITH includes an 8-week warm calling treatment that is delivered to older adults (racially and economically diverse, urban, suburban, and/or rural). At the start of the program, older adults are asked to reminisce about their life, and provide the treatment provider some information that can be built upon in subsequent call dosages (see graphic below).

Each week an older adult participant will receive a 20-30 minute "call dosage" from treatment providers that are trained in 1 of 2 protocols:

**(a) BE condition** which involves receiving call dosages from providers trained to foster **belongingness** and **empathy** (2 hours), grounded in the befriending literature, and narrative reminiscence. Aging Network Providers trained in BE provide a "small dose of sincere connection", through **narrative reminiscence**, and the "**befriending**" strategies.

While the majority of the warm calling of BE WITH centers on this basic connections intervention, there will also be individuals who need more than connection, but rather targeted intervention as approximately 20% of older adults receiving home and community-based services are at risk of suicide.

**(b) BE WITH condition** includes receiving call dosages from providers trained in BE + the aging variant of LivingWorks ASIST (Applied Suicide Intervention Skills Training). Those older adults assigned to this treatment condition will have both the connections intervention, as well as suicide interventions in the chance that one is needed.

**(c) control group** includes no treatment, or call dosages. Every two weeks graduate research students administer the measureset, just as they did for the 2 treatment conditions.

The same time intervals of outcome measures are administered across all 3 conditions.

## 2.

[figure not shown]
## 6.1.2 ADMINISTRATION AND/OR DOSING

Sixty trained providers (30 in each treatment condition) will provide the treatment to an assigned caseload of older adults via the phone. We are working with software developers (i.e. Friendlybuzz) who built a system to automatically record the audio files of the treatment dosages. Research team members will populate the caseloads of the older adult clients into Friendlybuzz for the treatment providers which enables the older adults contact information to remain protected (a requirement of our community partners). After caseloads are populated, treatment providers will call into the Friendlybuzz system; treatment providers push “1” for their first older adult, “2” for their second, and so on through their caseloads of 5-7 older adults each.

Treatment providers will not have any interaction with the older adults outside of providing the treatment. Every two weeks, after two call dosages (20-30 minutes each), data will be independently collected from the participants from trained graduate students at Georgia State University. This will go on for an additional 3 measurement occasions, for a total of 4 measurement occasions + the baseline (see graphic below).

Complete participation includes eight full call dosages between the average of 20-30 minutes each. Please see the graphic below for the complete treatment and assessment schedule.

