## 4. 3 OBJECTIVES AND ENDPOINTS

Objective	Metric/Variable	Hypothesis/role/endpoint	Analysis
-----------	-----------------	--------------------------	----------

Validate the BE WITH innovation	Reduce loneliness, and elevated suicidality, and increase the degree to which social needs are met	Over the 8-week treatment loneliness and suicide desire (as measured by the UCLA loneliness scale, Interpersonal Needs Questionnaire) will be significantly decreased, and the variable of social needs being met (as measured by the social provisions scale) will be increased for both treatment groups	Longitudinal growth modeling
Validate the BE WITH innovation	Three treatment conditions	Those older adult participants randomly assigned to the BE or BE WITH treatment condition will demonstrate significant improvements in mental health outcomes when compared with the control group	Longitudinal growth modeling
Validate the BE WITH innovation	Risk tier	Those older adults that start the 8-week treatment at medium or high risk will have statistically significant improvements when compared with those of low risk	Longitudinal growth modeling
Validate the BE WITH innovation	Provider effects	Determine if there is variance in outcomes as a result of the provider assigned. 60 providers were trained in either BE or BE WITH and carried caseloads of older adult clients enabling the nesting of effects to determine if there are individual or group level provider effects	Multilevel modeling
Validate the BE WITH innovation	Improved quality, frequency of empathic and suicide intervention best practice behaviors by trained NS providers	An augmented version of Gould's (2013) coding protocol was developed to quantitatively behaviorally code treatment call dosages.	independent quantitative behavioral coding, double coding, 2 protocols, inter-rater agreement, coefficient kappas

The main overarching objective of the clinical trial is to validate the 8-week BE WITH warm calling program, equipping the Aging Services Network (ASN) with proven skills to reduce social isolation, loneliness, and elevated suicidality, while also promoting social support/well-being. The goal of the validation objective is to garner the evidence needed to get the first such program on the National Council on Aging's Evidence Based Registry.

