
Reduction in loneliness, elevated suicidality, and improved social support/well-being for older adult clients
 
Validated constructs (see appendix D):
 
Loneliness (UCLA); Social Support (SPS); Suicide -- Risk (SBQ-R); Suicide Desire (INQ); Suicide Capability (FAD); Depression (PHQ); Anxiety (GAD); Distress (K6);
	
540 Clients, randomly assigned to 3 conditions. This includes the 2 tx conditions and a control that receive no calls
 
Stratified random sampling by 3 levels of loneliness and suicidality (low, medium, and high risk tiers)
	
Data collection for older adult participants:
 
 
· pre intervention (baseline)
 
· measurement occasions every 2 weeks (total of 5 measurement occasions)
 

Improved frequency of empathic and suicide intervention best practice behaviors by NS volunteers
 
Coded constructs: Adapted observation protocol.
	
60 Volunteers, randomly assigned to 2 conditions.
 
 
· BE training only
 
· BE WITH (BE training plus ASIST)
 
 
Those trained in BE will be offered ASIST after the study.
	
Preceding the intervention study, all volunteers receive BE (phone-based social connection) training. BE WITH volunteers will be given the standardized and manualized ASIST training (if they have previously received ASIST, they will be provided with the ASIST refresher training).

---	---	---

**Validated outcome measures** are essential for effective evaluation of any mental health or suicide prevention programming. While the social isolation, loneliness, and elevated suicidality constructs we will study are listed in the following table, the specific psychological scales that measure them are listed and explained in Appendix D. The comprehensive battery of assessments has been field tested and well received by older adults (Appendix D). We have also completed cognitive interviews (administered questions and sought feedback on the experience from older adults), and trained data collectors to use a conversational style in speaking with participants. Short forms of several of these measures will be completed weekly by the older adults and take 15 minutes to complete.

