4. Work effectively with ambivalence about dying, which involves listening closely for confusion, ambivalence, hesitancy to die by suicide as the person is sharing their story, and offering a 3rd option (to stay safe for right now) which is an easier choice to make, and more aligned with the reality that there is some hopelessness that things will never change, and offering this 3rd option creates space for the opportunity for some things to change
5. Developing mutually and agreed upon safety plans
6. Confirming actions (or asking the older adult to repeat the safety plan back to us that we have developed together to assess their degree of commitment to it)

Success of the training will be evaluated through pre, post and follow up training level outcome measures. Further interventionists will be objectively rated by trainers and supervisors.

The degree to which those trained adhere to the intervention will be managed with the use of the Friendlybuzz system. This enables the research team to track the fidelity and delivery of the intervention in real time. This system automatically records and transcribes each treatment dosage, while organizing the treatment dosages within each participant, nested within each treatment provider, along with the dates and duration of each of the treatment dosages.

There will not be any changes to any groups or clusters (i.e. treatment providers’ caseloads of older adult participants) unless there is a challenge with a treatment provider. If there is such a challenge,

we will first support the treatment provider through the weekly supervision groups. If the challenge persists or in the very rare case that we have a treatment provider that can no longer provide the treatment, any older adult participants that are assigned to the treatment provider will be re-baselined, and re-randomized to a new treatment provider. Again, we imagine this to be very rare.

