## 2. 6.3 MEASURES TO MINIMIZE BIAS: RANDOMIZATION AND BLINDING

We will use weighted stratified random assignment. After participants are baselined, we will score their data and assign them a risk tier (low, medium, high). Subsequently, we will randomize them to one of 3 conditions: BE condition, BE + ASIST condition, or control. Since the trial is being conducted in cohorts (waves), and to ensure the least amount of time between being baselined and starting the treatment, participants will be randomized one by one after they are baselined. The weighted component enables there to be equal representation of both risk tier and number of participants across all 3 treatment conditions within the confines of the ongoing nature of the trial.

At the time of baseline, participants are assigned 2 codes: one that is fully numeric, and another that is alphanumeric. The PI and graduate student(s) will have access to the unblinded data (i.e. both the older adults' names, codes, and baseline data) as the PI is supervising the process and a few graduate students will be helping with scoring, and the weighted stratified random assignment. The methodologist will only have access to the participants' codes and raw data. They will remain blind to ensure the most objective analysis of the data.

If a participant remains at elevated risk for suicide at the conclusion of the treatment, we will unblind them and report to their assigned case manager.

We will also use separate documents with participant codes only to track the following: treatment condition, rebaselines, any survey/measurement issues, risk tiers, etc. to ensure an additional level of rigor in protecting against any bias. Further, in all tracking files that the PI's research lab utilizes, only participant IDs will be utilized (i.e. tracking which participants are up for the next measurement occasion, etc.).

The only potential inadvertent unblinding that we could foresee would be with respect to the use of the Friendlybuzz system. The treatment providers do need to know the first names of the older adult participants, therefore ONLY their first names will be available. The data team, however, is completely distinct from the treatment team, and will not have access to the Friendlybuzz system.

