#### 2. 9.4.2 ANALYSIS OF THE PRIMARY ENDPOINT(S)

This validation study is a partially nested randomized controlled trial design (PN-RCT) with a two-level structure of clients (level-1) nested within callers (level-2) for the two treatment conditions which receive calls. Given that outcomes for older adults receiving calls from the same volunteer may be more similar than for those who receive calls from a different volunteer, the use of multilevel modeling can account for these data dependencies. Analyses will investigate the effect of treatment conditions (BE, BE WITH, and control) on post-intervention outcomes while controlling for baseline responses (prior to intervention). Furthermore, analyses will explore differences between treatment conditions in longitudinal trends of client state as well as how volunteers utilize specific intervention skills over time. For this longitudinal data, a lower level of nesting will be included in the analysis: weekly call and state data (level 1) nested within older adults (level 2) nested within volunteers (level 3). However, the PN-RCT design would only have levels 1 and 2 for the control group.

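### The provider-effects objective attributes outcome variance to the caller, but initial assignment to callers is not described and the model has no cohort or centre term, so wave or centre differences could appear as caller variance

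*Combined protocol and SAP*

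**What the plan says.** - **Objective.** The table in Section 3 includes a provider-effects objective, to be met by multilevel modelling: "Determine if there is variance in outcomes as a result of the provider assigned". That wording is causal.
- **What is randomised.** For participants, Section 6.3 says: "Subsequently, we will randomize them to one of 3 conditions: BE condition, BE + ASIST condition, or control". This is done one person at a time, in waves. For callers, Section 4.1 says: "60 Volunteers, randomly assigned to 2 conditions".
- **Matching participants to callers.** Section 6.1.2 says "Research team members will populate the caseloads of the older adult clients into Friendlybuzz", in caseloads of 5-7. The sentence explains how contact details are protected. It gives no rule for who is paired with whom. Section 6.2.1 says that participants of a caller who can no longer continue will be "re-baselined, and re-randomized to a new treatment provider". No section describes the first assignment.
- **Model.** Sections 4.1 and 9.4.2 give occasions within older adults within volunteers, with adjustment for baseline. There is no cohort or centre term, although Section 9.4.6 speaks of 4 cohorts and the synopsis of 25 senior centres.

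**The concern.** A caller variance component collects everything that the members of a caseload share and the model does not otherwise explain. It measures the provider only if nothing else is shared. Two things could be.

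- **Period.** The numbers give each caller one caseload for the whole trial. Section 6.3 wants little time between baseline and treatment, and Section 6.2.1 keeps caseloads unchanged unless a provider has difficulties. A caseload filled within one wave ties that caller to that wave.
- **Centre.** Callers are staff or volunteers of the 25 centres (Section 5.1), and helpers without ongoing contact with potential participants are excluded (Section 5.2). Same-centre pairing is plausible but not stated.

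At stake is one of the five rows of the objectives table: a calendar or centre difference could be reported as evidence that some callers do better than others.

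**Working it through.** **Plan's own figure.** Inputs from Section 9.2: effect .40, ICC .20, R² .50, caseload 6, Type I error .05 (two-sided assumed), power .80. For one called arm of k callers against an unclustered control of equal size:

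Var = ICC(1−R²)/k + (1−ICC)(1−R²)/(6k) + (1−R²)/(6k)

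With k = 15: .00667 + .00444 + .00556 = .01667, so .40/√.01667 = 3.10. The noncentral t with 14 df gives power .821, and 15 is the smallest k that reaches .80. That means 30 callers and 3 × 90 = 270 older adults, which matches Section 9.2. The plan's structure is therefore understood correctly.

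**Caseloads.** The final design has 2 × 180 = 360 called participants and 60 callers. 360/60 = 6, one caseload each. On average that is 60/4 = 15 callers per cohort and 60/25 = 2.4 per centre.

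**Test of caller variance with no true caller effect.** Let s be the share of residual variance common to all members of a caseload. The F test has 60 − 2 = 58 and 60 × 5 = 300 df. The F ratio is inflated by r = 1 + 6s/(1−s), so the false-positive rate is P(F > Fcrit/r). The critical values are 1.369 at .05 and 1.555 at .01, the level in Section 9.4.1.

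| s (assumed) | r | positive at .05 | positive at .01 |
|---|---|---|---|
| .01 | 1.061 | 9% | 2% |
| .02 | 1.122 | 15% | 4% |
| .05 | 1.316 | 41% | 19% |
| .10 | 1.667 | 82% | 62% |

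This formula treats the shared part as independent between caseloads, which is a simplification when there are only 4 waves.

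**Simulation with 25 centres and 4 waves.** 1000 trials per scenario, true caller variance zero, test at .05. Columns give the assumed centre + wave shares; brackets give the mean apparent caller ICC.

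| Caseloads and model | .02 + .02 | .05 + .02 | .05 + .05 |
|---|---|---|---|
| One centre and one wave; no added terms | 32% (.039) | 56% (.066) | 68% (.087) |
| Random caller within condition and wave; no added terms | 13% (.016) | 14% (.015) | 34% (.040) |

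Three other settings bring the apparent ICC to about 0 at all three pairs of shares:
- random caller within condition and wave, with a cohort term: 4-5% positive;
- one centre and one wave, with centre and cohort terms: 5-6% positive;
- caseloads mixed at random over centres and waves: about 5% positive.

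**Treatment-control contrast.** Randomisation to condition protects it from bias, and only precision is touched. With 30 callers × 6 against 180 controls, the variance is .2×.5/30 + .8×.5/180 + .5/180 = .00833. Suppose .05 of the .20 ICC were really centre variance. Random assignment to callers would give .15×.5/30 + .85×.5/180 + .5/180 = .00764. A centre term as well would give .15×.5/30 + .80×.5/180 + .95×.5/180 = .00736. The SE ratios are √(.00764/.00833) = .96 and √(.00736/.00833) = .94, a gain of 4-6%.

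**The case against.** **Staff choose the caseloads and only condition is randomised.** A reader might infer this from Section 6.1.2, but the documents do not support it. That sentence shows who enters caseloads into the system, not how pairings are made. The phrase "re-baselined, and re-randomized to a new treatment provider" in Section 6.2.1 may imply a random first assignment. It concerns replacement of a caller only and gives no procedure, so the question is open.

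**The objective will credit callers with centre and wave differences.** This is also too strong. It happens only if caseloads follow centre or wave. Section 6.1.2 rules out contact between callers and participants outside the calls, which weighs against same-centre pairing. If caseloads are mixed, there is no bias.

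**The design puts the problem beyond repair in analysis.** It does not. In the simulation, centre and cohort terms restored the error rate even with fully shared caseloads.

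**The figures are a worst case.** This largely stands. The shares are assumed and taken as fully shared, and baseline adjustment removes much of any stable centre difference in level. Differences in change remain. Section 9.4.9 itself names rurality as a possible moderator, so place may matter for response.

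**The consequence is limited.** This stands too. Provider effects are in the Section 3 table but not among the Section 9.1 hypotheses.

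**Conclusion.** The concern holds in a conditional form. The plan reads caller variance causally, describes no initial assignment to callers, and has no term to separate caller from cohort or centre. The wave route is the more likely one, because the numbers allow one caseload per caller; the centre route is an inference from eligibility rules that point in both directions.

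The false-positive rates depend on shared variance that the documents do not give. They run from barely above nominal at a 1% share to most trials at 10%, and to nominal if caseloads are mixed. Using the .01 level lowers the rates but leaves them well above 1% once the share is 2% or more.

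The point concerns the provider-effects objective alone. A reader might infer that the comparison of called arms with control is compromised. The documents do not support that, since condition is randomised.

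**What to change.** 1. Add cohort (fixed) and senior centre (random effect, crossed with caller) to the provider-effects model, and record both for every participant. This is the main change. A cohort term alone would leave the centre part if caseloads follow centres.
2. State how participants are first assigned to callers, and reconcile this with the re-randomisation wording in Section 6.2.1.
3. Where feasible, draw the caller at random among those of the allocated condition with an open place in that cohort. The cohort term is needed even then.
4. If staff choose caseloads, report the result as variation between caseloads and do not attribute it to the provider.

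**Cost.** The model is slightly harder to fit. If every caseload came from a single centre and wave, and all 25 centres supplied callers, fitting both as fixed terms would leave about 58 − 24 − 3 = 31 df for callers, so a true caller effect would be harder to detect. That loss is the honest price of separating the sources.

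The random draw is the debatable part. It reduces freedom to pair callers with clients of their own centre, which the protocol may value: connection within one's community is a core component of the BE training in Section 6.2.1. Section 3 also describes caller training and caseloads in the past tense, so a change to allocation may come too late. Items 1, 2 and 4 would still be possible.

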## 8.

## 1.

## 6.2 FIDELITY

## 1. 6.2.1 INTERVENTIONIST TRAINING AND TRACKING

The five core components to the BE training include:

1. **reciprocity**: the feeling that both parties are benefiting
2. **intimacy**: willingness to share deeply (superficial sharing at first helps build the relationship, but deeper sharing is what leads to positive outcomes)
3. **reliability & respect** (calling at the time you say you are going to call creates consistency and reliability, and that the older adult matters)
4. **proximity**: feeling more connected to people within your community
5. **autonomy**: feeling both parties are willingly participating with each connection

Analogous to CPR (lay providers equipped to help someone that is drowning), anyone can learn “suicide first aid”, or LivingWorks ASIST. Persons trained in ASIST connect directly with the older adult at risk through a six-step model called the *Pathway for Assisting Life (PAL)*. The PAL model matches *six needs* of the older adult-at-risk with *six tasks* of the caregiver.

Persons-at-risk (and helpers) often perceive only two options: (a) to die by suicide, or (b) to live. Choosing to live or die can be a tough choice when an individual is struggling with suicidality. The ASIST training introduces a third option, which is to *stay safe for now*. Through engaging the PAL model those trained help the patient-at-risk identify ambivalence about dying, confusion, and even reasons for living. This is a little miracle that saves lives, as it removes the dichotomy of life/death, and ASIST training equips lay providers to do this. Caregivers are not taking away the choice to suicide, and the person’s autonomy. Rather, **through** the intervention, caregivers return autonomy to persons-at-risk by helping them identify *their own reason(s) to live*, and link that to a safety plan that puts suicide on hold for the moment, which may turn into staying safe in the long term. The 6 steps of the PAL include:

1. Notice and explore invitations (i.e. voluntary stopping of eating and drinking, withholding medical treatment, withdraw, talking directly about suicide, etc.)
2. Asking directly about suicide
3. Not only listen, but sincerely hear the story about suicide
4. Work effectively with ambivalence about dying, which involves listening closely for confusion, ambivalence, hesitancy to die by suicide as the person is sharing their story, and offering a 3rd option (to stay safe for right now) which is an easier choice to make, and more aligned with the reality that there is some hopelessness that things will never change, and offering this 3rd option creates space for the opportunity for some things to change
5. Developing mutually and agreed upon safety plans
6. Confirming actions (or asking the older adult to repeat the safety plan back to us that we have developed together to assess their degree of commitment to it)

Success of the training will be evaluated through pre, post and follow up training level outcome measures. Further interventionists will be objectively rated by trainers and supervisors.

The degree to which those trained adhere to the intervention will be managed with the use of the Friendlybuzz system. This enables the research team to track the fidelity and delivery of the intervention in real time. This system automatically records and transcribes each treatment dosage, while organizing the treatment dosages within each participant, nested within each treatment provider, along with the dates and duration of each of the treatment dosages.

There will not be any changes to any groups or clusters (i.e. treatment providers’ caseloads of older adult participants) unless there is a challenge with a treatment provider. If there is such a challenge,

we will first support the treatment provider through the weekly supervision groups. If the challenge persists or in the very rare case that we have a treatment provider that can no longer provide the treatment, any older adult participants that are assigned to the treatment provider will be re-baselined, and re-randomized to a new treatment provider. Again, we imagine this to be very rare.

